Effects of Virtual Reality on Women Undergoing Breast Reconstruction

[figure not shown]
VR 4 BR

A Pilot Study

Principal Investigator: **[name]**
Cedars-Sinai Medical Center
[name]

Sub-Investigator(s)	Department/Division
[name]	Health Services Research
[name]	Health Services Research
[name]	SOCCI CRO
[name]	Surgery/Breast Center
[name]	Surgery/Breast Center
[name]	Surgery/Breast Center
[name]	Surgery/Breast Center
[name]	Statistician
[name]	Surgery/Breast Center

STUDY SCHEMA

Primary endpoint: Opioid use

BACKGROUND AND RATIONALE

1.1 Disease Background

Pain management is a crucial aspect of study participant-centered care. However, the current increase in prescription opioid misuse and overdose fatalities is evident to the dangers of these medications. According to the 2016 National Survey on Drug Use and Health, an estimated 11.8 million people misused opioids in the previous year [1]. Factors such as diagnosis distress, invasive procedures, as well as pain related to therapies can make cancer study participants undergoing therapies vulnerable to opioid misuse [2-4]. Postoperative prescription opioid misuse is well-documented in the literature. About 6% opioid-naïve study participants undergoing noncancer procedures develop new persistent opioid use [5]. For study participants with cancer undergoing curative-intent surgery, the risk of new persistent opioid use is 10.4% [6]. As for many types of surgery, opioids are used for pain control after mastectomy and breast reconstruction. Marcus et al. utilized health benefits claims to identify 4,113 women who underwent mastectomy for breast cancer and immediate breast reconstruction between 2010 and 2014. All study participants were opioid-naïve. Based on the pharmacy claims data after breast reconstruction, 90 percent of study participants filled an opioid prescription. Ten percent of these women continued to fill an opioid prescription three months later. For women diagnosed with anxiety and those who experienced some type of complication (such as infection) prolonged opioid use was more common [7].

Most opioid prescribing guidelines focus on study participants with chronic pain, rather than postoperative pain. To our knowledge, there is no guidelines for opioids prescription following mastectomy and reconstruction procedures.

Rising rates of opioids prescription contribute to the opioid epidemic. The threat of dependence and prolonged use of opioids prescribed after surgery cannot be overemphasized. Alternative, non-pharmacological interventions to control pain after surgery seem to be the best approach to address this problem. Virtual Reality (VR) can be a viable approach.

VR provides immersive, realistic, three-dimensional experiences that “transport” users to novel environments. Thus, it has the potential to alleviate negative aspects of care by providing multi-sensory information and allowing study participants to “escape” to pleasant locations and realities when they are most distressed. VR offers an ability to temporarily alter the way study participants experience their environment, facilitating distraction from symptom triggers, increasing sense of control, and providing a safe coping mechanism. By providing an alternative to excess opioid use for pain, VR may not only ameliorate acute symptoms, but also diminish opioid-related adverse effects such as overdose and opioid use disorder, and reduce hospital length of stay.

Feasibility of VR interventions in a medical setting has been documented in the literature [8]. To our knowledge, effects of VR in controlling pain and study participant’s satisfaction for women undergoing mastectomy followed by implant-based reconstruction has not been studied.

2.0 STUDY OBJECTIVES

Primary Objectives

2.0.2 To estimate the effect of utilizing VR on reducing opioid use in study participants undergoing mastectomy with implant-based reconstruction compared to the control group

2.1 Secondary Objectives

2.1.1 To evaluate the effects of VR upon:

- a) Pain scores
- b) Study participant satisfaction
- c) Length of stay

2.2 Endpoints

- **Primary Efficacy Endpoint**
Opioid use
- **Secondary Efficacy Endpoints**
Pain score
Patient satisfaction
Length of stay

3.0 STUDY DESIGN

We will conduct a pilot study of VR non-opioid management for women undergoing mastectomy and implant-based reconstruction. Study participants will receive specialized VR interventions, administered via VR headsets, to manage pain.

Historical control patients of the study investigators, who have undergone mastectomy and implant-based reconstruction between October 2008 to October 2018, will be identified by the Cancer Registry, according to the study eligibility criteria, and matched based on the following criteria:

- Age and gender
- Prophylactic or cancer
- Pre- or post-pectoral approach
- Sentinel biopsy, axillary dissection, or no nodal surgery
- Use of Paravertebral Block Analgesia (PVB)
- Neoadjuvant therapy or not

The matching will be done by the study statistician. Prior to sending the log to the statistician, the Cancer Registry database will be deidentified by the study staff and coded to ensure patient confidentiality. This portion of the study this is a retrospective data analysis and a waiver of consent and HIPAA authorization will be requested to review and collect data from these patients' medical records.

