6.0 STUDY PROCEDURES

6.1 Screening/Baseline Procedures

6.1.1 Informed Consent

Eligible subjects will be identified by the investigators and research staff according to the eligibility criteria. Subjects will be asked to sign and date the Informed Consent and HIPAA Authorization form after receiving a complete explanation of the research study including risks, benefits, and alternatives to participation. Eligible subject must have the ability to understand and the willingness to sign a written informed consent document.

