8.0 STATISTICAL CONSIDERATIONS

8.1 Sample Size

This is an exploratory pilot study to estimate the effect of VR on opioid use during the stay. We will enroll 20 eligible patients to this study. We will include data from 20 patients for the historical control portion of the study matched 1 to 1 on age, surgery type, use of neoadjuvant therapy, and use of paravertebral block analgesia. Assuming a standard deviation of 1, a sample size of 20 matched pairs would produce a confidence interval with a distance from the mean to the limits that is equal to 0.468 for the difference in requested pill count.

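### Surgeon is in neither matching list nor the paired analysis, so a systematic difference in surgeon mix between VR participants and controls could pass for a VR effect

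*Combined protocol and SAP*

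**What the plan says.** Section 3.0 (Study Design) describes the comparators as "Historical control patients of the study investigators" who had the operation "between October 2008 to October 2018, will be identified by the Cancer Registry". The list of sub-investigators at the front of the protocol has five entries under "Surgery/Breast Center".

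Two lists govern the matching:
- **Section 3.0** has six items. It starts with "Age and gender" and goes on to indication (prophylactic or cancer), pectoral approach, nodal surgery, paravertebral block and neoadjuvant therapy.
- **Section 8.1 (Sample Size)** is shorter: "matched 1 to 1 on age, surgery type, use of neoadjuvant therapy, and use of paravertebral block analgesia".

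Neither names the surgeon. Section 3.0 also says that study staff de-identify and code the registry data before the statistician does the matching.

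On accrual, section 8.1 states "We will enroll 20 eligible patients to this study", and section 6.1.1 states "Eligible subjects will be identified by the investigators and research staff according to the eligibility criteria". The Data Analyses/Study Endpoints section plans a paired t test on pill count, with confidence intervals in each group for pills, pain scores, satisfaction and length of stay. It has no surgeon term, stratification or surgeon-based sensitivity analysis.

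**The concern.** The comparison is not randomised, so matching is the only design feature that controls confounding. The listed factors show an intention to hold the operation and its analgesic setting constant. The surgeon belongs with them, because opioid ordering and discharge timing may differ between surgeons even for the same procedure.

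Restricting controls to the investigators' own patients keeps out other surgeons' practice, but it does not make the mix of investigators the same in the two groups. With only 20 VR participants, the shares could differ appreciably from those in a ten-year control pool. Two outcomes are most exposed: the primary opioid comparison, and length of stay, which depends directly on when a patient is discharged.

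Section 8.1 gives estimation of the VR effect on opioid use as the purpose of the pilot. A shift in that estimate from surgeon mix would therefore bear on the study's main product. It could exaggerate a VR effect or hide one.

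**Working it through.** **Inputs from the documents.** 20 pairs; "Assuming a standard deviation of 1, a sample size of 20 matched pairs"; stated half-width 0.468; paired t test. The confidence level is not stated.

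**Step 1. Reproduce the plan's figure.** Half-width = t(0.975, 19 df) × SD / √n = 2.093 × 1 / √20 = 0.468. This matches. The alternatives do not: the normal quantile gives 0.438, a 90% two-sided t interval 0.387, and an unpaired comparison with 20 per group 0.640. So the interval is two-sided 95%, and the SD of 1 is that of the paired difference. The figure is correct and is not in dispute.

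**Step 2. Bias formula.** Bias = sum over surgeons of (share in VR group − share in controls) × surgeon's mean outcome. If one surgeon's patients differ from the rest by a gap D, and that surgeon's share differs between the groups by s, this becomes bias = s × D.

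**Step 3. Assumed range.** The documents give neither s nor D, so both are assumptions. D is in SDs of the paired difference. The last column is the chance of a two-sided 5% rejection when VR has no effect. It comes from the noncentral t distribution with 19 df and noncentrality bias × √20, with the SD held at 1.

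| Imbalance s | Gap D | Bias | Bias / 0.468 | False-positive rate |
|---|---|---|---|---|
| 0 | any | 0 | 0% | 5% |
| 0.20 | 0.5 | 0.10 | 21% | 7% |
| 0.40 | 0.5 | 0.20 | 43% | 14% |
| 0.40 | 1.0 | 0.40 | 85% | 40% |

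A 40-point imbalance would be, for instance, 60% of VR participants against 20% of controls.

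**Step 4. Sensitivity to the scale.** If D is instead in SDs between patients, and the two members of a pair are uncorrelated, the patient-level SD is 1/√2 = 0.71. The two 40-point rows then become 0.40 × 0.5 × 0.71 = 0.14 (30%) and 0.40 × 1.0 × 0.71 = 0.28 (60%).

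**Step 5. Cost of restricting to same-surgeon pairs.** If 15 of the 20 pairs share a surgeon, the half-width at SD 1 is t(0.975, 14 df) / √15 = 2.145 / 3.873 = 0.554. That is 0.554 / 0.468 = 1.18, or 18% wider.

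**The case against.** The strongest reply is that the premise is inferred. Surgery/Breast Center is a department label. The documents do not say how many of the five operate, how cases are shared, or whether their ordering or discharge habits differ. All of this stands, and it is why no size can be claimed. If one surgeon does nearly all the cases, the problem is negligible.

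A reader might infer that accrual will concentrate on one or two surgeons who favour VR. The documents do not support that: section 6.1.1 has investigators and research staff identifying participants by the eligibility criteria, and nothing indicates selective accrual.

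Some control already exists. Controls are limited to the investigators' own patients, and section 3.0 matches on pectoral approach, nodal surgery and paravertebral block, through which part of any surgeon difference would act. This narrows the concern to the remaining imbalance in mix but does not remove it. Pills requested is also partly patient-driven, although the orders in place can still affect it.

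A reader might also infer that the confidence interval ignores surgeon differences altogether. It misses only a systematic difference in mix. Haphazard cross-surgeon pairing widens the spread of the paired differences, and the t interval reflects that.

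Finally, mandatory exact matching on surgeon could be a poor trade with 20 pairs and six listed items. It might force looser age matches or controls from earlier in the window, and discarding unmatched pairs loses precision. That objection stands against exact matching, but not against a preference for same-surgeon controls.

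**Conclusion.** The concern holds as a possible bias of unknown size and direction. The documents establish that controls come from several investigators' patients, that surgeon is in neither matching list, and that the analysis does not adjust for it. They do not establish that surgeon mix or surgeon practice differs, and both must differ for a bias to arise.

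Under the assumptions shown, the bias runs from zero with an equal mix, through 21% of the half-width in a mild case, to 85% in a strong one. The upper figure should not be read as the expected size: it rests on an assumed 40-point imbalance and an assumed 1.0 SD gap, and it falls to 60% if the gap is in patient-level SDs with uncorrelated pairs.

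This is an exploratory pilot, and the 0.468 is arithmetically sound. The point is a cheap improvement to the matching, not a fault that invalidates the design. Change in practice over 2008-2018 is a separate matter that surgeon matching would not solve.

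**What to change.** 1. Keep a coded surgeon identifier in the de-identified matching log. Define it for the mastectomy and, where available, for the reconstruction component. This has to be settled before the log goes to the statistician; without the code, neither matching nor later adjustment may be possible from that log.
2. The matching lists in 3.0 and 8.1 differ and need reconciling anyway. In the same edit, add surgeon as a preferred factor: choose a same-surgeon control whenever one meets the other matching criteria.
3. Report surgeon mix by group.
4. Keep all 20 pairs in the primary analysis, and add a sensitivity analysis restricted to same-surgeon pairs.

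**Cost.** One coded field, wording changes in 3.0, 8.1 and the data analyses section, and one extra analysis. The downsides are a somewhat smaller control pool per participant, possibly looser age matches, and a wider interval in the sensitivity analysis (0.554 in the 15-pair example). The planned 0.468 for the primary analysis is unchanged if the SD of the paired difference stays at 1.

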4.0 PATIENT ELIGIBILITY

4.1 Inclusion Criteria

4.1.1 Age \geq 18 years

4.1.2 Women who plan to undergo mastectomy and implant-based reconstruction

4.1.3 Written informed consent obtained from subject and ability for subject to comply with the requirements of the study.

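### The matching list in section 3.0 omits unilateral versus bilateral mastectomy and 8.1 leaves surgery type undefined, so discordant pairs are possible; they bias the VR comparison if the bilateral share differs between cohorts

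*Combined protocol and SAP*

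**What the plan says.** Section 3.0 (Study Design) draws historical controls from October 2008 to October 2018 under the study's eligibility criteria and itemises the matching factors: age and gender, indication ("Prophylactic or cancer"), pectoral approach, nodal surgery ("Sentinel biopsy, axillary dissection, or no nodal surgery"), paravertebral block and neoadjuvant therapy. The statistician does the matching from a log that study staff have coded and deidentified.

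Section 8.1 (Sample Size) gives a shorter list. The 20 controls are to be "matched 1 to 1 on age, surgery type, use of neoadjuvant therapy, and use of paravertebral block analgesia". Surgery type is not defined there or anywhere else.

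Inclusion criterion 4.1.2 reads "Women who plan to undergo mastectomy and implant-based reconstruction", with no restriction to one side or both. Neither unilateral nor bilateral appears as a word in the document.

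The analysis section (9.2, Data Analyses/Study Endpoints) compares pill count by a paired t test. For pain scores, satisfaction and length of stay it plans confidence intervals in each cohort. It describes no covariate adjustment or stratification.

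**The concern.** There is no randomisation, so the comparison depends on pairs being alike in what drives postoperative opioid need. The plan already matches on operative features that plausibly affect pain: implant plane, nodal surgery and nerve block. The number of breasts operated on is at least as direct a measure of surgical extent, yet the detailed list leaves it out.

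No listed factor fixes it. A woman with cancer in one breast counts as a cancer case whether one or both breasts are removed. Pectoral approach, nodal surgery and nerve block do not determine the number of breasts either. The statistician can match only on fields supplied in the coded log, and laterality is not named as one.

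At stake is the study's stated purpose, an estimate of the effect of VR on opioid use. An imbalance in laterality would be credited or charged to VR, and the planned analysis has no step that would show it or correct it. The same imbalance would affect the cohort comparisons of pain and length of stay.

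**Working it through.** **Inputs from the plan.** Section 8.1 gives 20 pairs ("a sample size of 20 matched pairs would produce a confidence interval"), an SD ("Assuming a standard deviation of 1") and a precision ("equal to 0.468 for the difference in requested pill count"). The confidence level is not stated; 95% two-sided is assumed because it reproduces the figure.

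**Inputs that are assumptions.** D is the extra opioid use from bilateral surgery, in units of that SD, shown for 0.5 and 1. pV and pC are the bilateral shares in the VR and control groups. The documents give none of these. Pairing is taken as independent of laterality.

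**Step 1: the plan's own figure.** t(0.975, 19 df) × SD / √n = 2.093 × 1 / √20 = 0.468. This agrees with 8.1, so the point is about confounding and not arithmetic. The agreement also shows that the SD of 1 was used as the SD of the paired difference.

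**Step 2: bias in the mean paired difference.** Each pair's difference includes D × (VR bilateral indicator − control bilateral indicator), whose mean is (pV − pC) × D.

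| pV, pC | Bias, D = 0.5 | Bias, D = 1 | Share of 0.468 |
|---|---|---|---|
| 0.5, 0.5 | 0 | 0 | 0% |
| 0.6, 0.5 | 0.05 | 0.10 | 11% to 21% |
| 0.5, 0.3 | 0.10 | 0.20 | 21% to 43% |
| 0.7, 0.4 | 0.15 | 0.30 | 32% to 64% |

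The sign follows the sign of the gap, which the documents do not indicate.

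**Step 3: can a gap arise by chance?** Suppose the underlying share is 50% in both groups of 20. The difference in counts is distributed as Binomial(40, 0.5) − 20. The probability that it is 4 or more in either direction (20 points or more) is about 27%.

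**Step 4: variance when the shares are equal.** With common share p, laterality contributes 2p(1 − p)D² to the variance of the paired difference. At p = 0.5 this is 0.5D², and about 10 of 20 pairs are discordant. The effect on the half-width depends on what the SD of 1 represents.

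- If it excludes laterality variation, the half-width is 0.468 × √(1 + 0.5D²): 0.468 × 1.0607 = 0.496 at D = 0.5, and 0.468 × 1.2247 = 0.573 at D = 1.
- If it already includes that variation, the half-width stays at 0.468. Exact matching on laterality would narrow it to 0.468 × √(1 − 0.5D²): 0.438 at D = 0.5, and 0.331 at D = 1.

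p = 0.5 is the worst case for this term; p = 0.2 gives 0.32D². If laterality is associated with a factor already matched, such as indication or nodal surgery, fewer pairs are discordant than independent pairing implies.

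**Step 5: reach.** Step 4 applies only to pill count, the one endpoint analysed by paired difference. Step 2 carries over to the cohort comparisons of pain and length of stay, with D replaced by the effect of bilateral surgery on that endpoint.

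**The case against.** Several points on the other side stand, and they limit what can be claimed.

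- **Bias is conditional.** A reader might infer that the VR effect is biased simply because laterality is unmatched. The documents do not support that: bias needs different bilateral shares, and nothing in the plan says the shares differ or in which direction.
- **Section 8.1 may intend to cover it.** A reader might infer that both lists demonstrably omit laterality. For 8.1, what can be shown is an undefined term that does not agree with the list in 3.0. Surgery type could be meant to include laterality, but the only operative details itemised in 3.0 are pectoral approach and nodal surgery.
- **The interval need not widen.** The SD of 1 is assumed for pairs matched without laterality being named. On its natural reading it may already contain laterality variation, in which case 0.468 stands.
- **The inputs are illustrative.** The documents give no D, and a small D would make the problem small. Even a bias of 0.10 to 0.20 lies inside the planned half-width of an exploratory pilot.
- **Matching has a price.** Section 3.0 already has six matching items, the size of the control pool is not given, and another exact factor could force looser matches on the rest.

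These points reduce the size of the problem and argue for a fallback. They do not remove the omission from 3.0. A bias smaller than the half-width still shifts the estimate that the pilot exists to produce, and the interval does not account for it.

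**Conclusion.** The point holds in conditional form. Following section 3.0 as written, a one-sided operation can be paired with a two-sided one, and no later step in the analysis corrects this.

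If bilateral shares differ, the opioid comparison is biased by the share gap times D. An assumed 20-point gap and D of 0.5 to 1 SD give 0.10 to 0.20, or 21% to 43% of the stated half-width. If shares are equal, the cost is avoidable variance in the paired pill-count difference only, and whether the half-width exceeds 0.468 depends on what the assumed SD contains.

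The direction and actual size cannot be determined from the documents. The conclusion rests on one clinical premise that the plan does not state: that bilateral surgery affects opioid use, pain or stay. That is plausible and consistent with the operative features the plan already matches on. The gap should be closed before matching, but it does not invalidate the pilot.

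**What to change.** Before matching begins:

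1. Add to the list in section 3.0: unilateral or bilateral mastectomy (operation performed), taken from the operative record in both groups, and include that field in the coded log sent to the statistician.
2. Define surgery type in section 8.1 so that it names the same surgical factors as 3.0.
3. State that if no exact match on laterality can be found for a participant, laterality will be reported by cohort and a laterality-adjusted sensitivity analysis added for the opioid comparison.

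The planned 20 pairs and the 0.468 calculation need not change. The cost is a few lines of text and one more field abstracted for every candidate control, not only for the 20 selected. The pool of eligible controls for each participant also shrinks. Ten years of cases should help, but the pool size is not stated, which is why the fallback in item 3 is needed.

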4.0 PATIENT ELIGIBILITY

4.1 Inclusion Criteria

4.1.1 Age \geq 18 years

4.1.2 Women who plan to undergo mastectomy and implant-based reconstruction

4.1.3 Written informed consent obtained from subject and ability for subject to comply with the requirements of the study.

